4.4 Post therapy Assessment

This is not a therapeutic study, but rather a prospective imaging correlate study.

4.5 Post therapy Intervention

- Serum creatinine will be checked 1 week (-3 days/+7 days) after the procedure and again at 1 month (+/- 10 days) after procedure.

4.6 Duration of Therapy

CT Angiogram will be obtain without exceeding the limits of IV contrast before SRS administration (SRS is not a part of this protocol), which typically be completed in one day. CT Angiogram will proceed unless:

- Subject decides to withdraw from the study, OR
- General or specific changes in the patient's condition render the subject unacceptable for further treatment in the judgment of the stereotactic team.

4.7 Duration of Follow Up

Nearly all the information needed for the protocol will be collected on the day of the procedure. Only AEs reported to Radiation Oncology discipline per study calendar will be captured and assessed. No follow up of AVM outcome is assessed as part of this protocol.

4.8 Removal of Subjects from Protocol Therapy

Subjects will be removed from therapy when any of the criteria listed in Section 5.5 apply. Notify the Principal Investigator, and document the reason for study removal and the date the subject was removed in the Case Report Form.

5.0 STUDY PROCEDURES

5.1 Screening/Baseline Procedures

Assessments performed exclusively to determine eligibility for this study will be done only after obtaining informed consent. Assessments performed for clinical indications (not exclusively to determine study eligibility) may be used for baseline values even if the studies were done before informed consent was obtained.

All screening procedures must be performed within 90 days prior to registration unless otherwise stated. The screening procedures include:

5.1.1 Informed Consent

5.1.2 Medical history

Complete medical and surgical history

5.1.3 Review subject eligibility criteria

5.1.4 Review previous and concomitant medications

5.1.5 Physical exam

Vital signs (temperature, pulse, respirations, blood pressure), height, weight, and neurological exam

5.1.6 Adverse event assessment

See section 7 for Adverse Event monitoring and reporting.

5.1.7 Serum Creatinine

5.1.8 Pregnancy test (for females of child bearing potential)

See section 3.1.6.1 for definition.

5.2 Follow-up Procedures

This is not a treatment study, and the subject will not be followed for AVM outcome for the purpose of this study. Serum creatinine value will be checked 1 week (-3 days/+7 days) after the procedure and 1 month (+/- 10 days) after the procedure.

5.3 Time and Events Table

	Pre-study ¹	Day 0	1 Week (-3 days, +7 days)	1 Month (+/- 10 days)
Informed Consent	X			
History and PE	X			
Serum Creatinine ²	X		X	X
Interventional Cerebral Arteriography		X		
CT Angiogram		X		
Adverse Event Assessment		X ³	X ³	X ³

1 – All screening procedures must be performed within 90 days prior to registration unless otherwise stated

2 – Within 30 days of SRS procedure

3 – Only if subject receives more than the recommended dose of contrast

5.4 Removal of Subjects from Study

Subjects can be taken off the study treatment and/or study at any time at their own request, or they may be withdrawn at the discretion of the investigator for safety, behavioral or administrative reasons. The reason(s) for discontinuation will be documented and may include:

- 5.4.1 Subject voluntarily withdraws from treatment (follow-up permitted);
- 5.4.2 Subject withdraws consent (termination of treatment and follow-up);
- 5.4.3 Subject is unable to comply with protocol requirements;
- 5.4.4 Subject demonstrates disease progression (unless continued treatment with study drug/treatment is deemed appropriate at the discretion of the investigator);
- 5.4.5 Subject experiences toxicity that makes continuation in the protocol unsafe;
- 5.4.6 Treating physician judges continuation on the study would not be in the subject's best interest;
- 5.4.7 Subject becomes pregnant (pregnancy to be reported along same timelines as a serious adverse event);
- 5.4.8 Development of second malignancy (except for basal cell carcinoma or squamous cell carcinoma of the skin) that requires treatment, which would interfere with this study;
- 5.4.9 Lost to follow-up. If a research subject cannot be located to document survival after a period of 2 years, the subject may be considered "lost to follow-up." All attempts to contact the subject during the two years must be documented

6.0 Measurement and evaluation of AVM targets

6.1 AVM Target

Quantitative analysis of the accuracy of the experimentally generated targets will be performed in this study based on two established methods of segmentation geometric accuracy evaluation (see section 6.1.2).

6.1.1 Definitions

Target: Target is the AVM nidus (figure 1) excluding the feeding artery and draining vein or hemangioma, if present.

Reference Target lesion: AVM nidus identified using interventional cerebral arteriography superimposed to MRI of brain +/- CT angiography (CTA), per treatment team discretion that is used in the actual SRS treatment.

CTA Target lesion: AVM nidus identified using CT angiogram of the brain alone, at a later date (greater than one month later) in a blinded manner, by the Neurosurgeon who contoured the reference target lesion.

MRI Target lesion: AVM nidus identified using MRI of the brain alone, at a later date (greater than one month later) in a blinded manner, by the Neurosurgeon who contoured the reference target lesion.

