Objectives	Evaluate whether a treatment plan based on CT angiography can accurately and precisely identify the target nidus as compared to standard cerebral arteriography fused to MRI.
Number of Subjects	14
Diagnosis and Main Inclusion Criteria	Patients with AVM requiring SRS, age \geq 10 years. Size $\leq 3.5\text{cm}$; $\leq 12\text{cc}$
Study Product(s), Dose, Route, Regimen	Radiation, Stereotactic Radiosurgery with Gamma Knife, using standard of care, as directed by the treating Radiation Oncologist and Neurosurgeon.
Duration of administration	One day procedure
Reference therapy	Radiation, Stereotactic Radiosurgery of AVM using standard of care approach and MRI
Statistical Methodology	The target volume generated by IR angiogram will be compared to the target volume generated by CT angiogram using the Sorensen-Dice coefficient and surface to surface distance.

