1.2 Stereotactic Radiosurgery (SRS)

SRS is an effective and minimally invasive approach compared to surgery. Its main drawback is the longer duration of time to achieve total obliteration of the AVM, ranging from six months to five years after the procedure⁵. Although the effect of SRS is not immediate, SRS is a preferable treatment option for patients with AVMs that are not surgically accessible or in patients with comorbidities that make them poor surgical candidates. In SRS, a potent dose of highly conformal radiation is delivered in a single fraction to the target nidus, leading to elimination in blood flow through the nidus in 40-80% of patients depending on AVM size⁶. SRS of AVM leads to the closure of the malformed vascular lumen, likely due to endothelial cell proliferation and fibrosis. In many centers that perform SRS, patients with AVM only undergo T1-weighted MRI image with gadolinium contrast to delineate the target volume. While MRI provide excellent soft tissue information, the AVM nidus is often difficult to be distinguished from the draining vein or a hematoma in the case of a previous hemorrhage, which leads to a treatment target considerably larger than the nidus itself. Other centers use volumetric CT angiograms to define the target.

At our institution, we routinely perform interventional cerebral arteriography on the day of the SRS procedure for improved target delineation. Following image acquisition, an neurointerventional specialist manually delineates the AVM nidus on the planar angiogram images; these images are stereotactically fused with the MR images. The nidus of the AVM is then contoured by the Neurosurgeon using the mutual information, to distinguish the AVM from a draining vein or the surrounding hematoma if there was prior hemorrhage. This extra information from the angiography allows the target volume to be significantly smaller compared to targets generated solely from MRI sequence, allowing us to spare the surrounding normal brain parenchyma. Even though the addition of angiography is time consuming and requires multi-modality team care, this approach has allowed our institution to treat the smallest possible target, yet achieve excellent obliteration rates of AVM with very low toxicity from the procedure. At our institution we also use CT angiogram at the treatment team's discretion to further enhance the accurate delineation of the final treatment

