1.3 Rationale for the Protocol

While interventional cerebral arteriography is the gold standard for the diagnosis, treatment planning and follow up of AVM, it is an invasive procedure that comes with the risk of stroke (< 1 %), arterial dissection (< 0.5%), transient ischemia (< 3 %) and bleeding at the puncture site⁷⁻¹¹. The risk of developing neurologic complications after the procedure appears to be elevated in patients with atherosclerotic cerebrovascular disease or cardiovascular disease, patients older than 55 years of age, and with fluoroscopic time beyond 10 minutes^{11,12}. Interventional cerebral arteriography is also the gold standard in the diagnosis of acute ischemic stroke. Nevertheless, it is rarely performed nowadays as the primary diagnostic test in the acute setting. The main reason for the change in practice pattern is the advent of the noninvasive techniques such as CT and MR angiography and duplex and transcranial Doppler ultrasound that can rapidly visualize intracranial arterial disease. While SRS of AVM is not performed in the acute setting, performing a noninvasive angiogram instead of interventional arteriography will reduce the total treatment time by three to four hours. Such reduction in the procedure time will likely improve patient comfort and satisfaction as it will reduce the time these patient would need to wear the uncomfortable stereotactic headframe.

While noninvasive imaging with CT and MR angiography have still not replaced interventional cerebral arteriography, technical advances are allowing these modalities to serve as powerful adjuncts (reviewed in ¹³). In fact,

interventional cerebral arteriography only provides two-dimensional (2D) spatial information when combined with the gamma knife treatment planning system and requires an MRI of the brain for the 3D information (Figure 2) while CT or MR angiography provide 3D information that could be used in the treatment planning of SRS. However, the use of these reconstructed angiographic images for treatment planning of SRS has not been validated against interventional cerebral arteriography.

Major risk factor for contrast agent-induced nephropathy is underlying renal dysfunction¹⁴. If a patient's renal function

[figure not shown]

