In summary, we propose to evaluate whether a target volume based on CT angiography can serve as a reliable substitute for a target based on interventional cerebral arteriography. Patients on this protocol will still get treated based on target generated by interventional cerebral arteriography but also receive CT angiography. If the target volume based on CT angiography are adequate compared to their invasive counterpart, future investigators may selectively omit performing interventional cerebral arteriography in the treatment planning for SRS of AVM. Use of CT angiography may lead to reduction in the risk from the procedure and cost, improve the efficiency of the treatment process ideally without compromising the success of the procedure, with greater patient comfort and satisfaction.

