2.0 STUDY OBJECTIVES

2.1 Primary Objective

To evaluate whether target(s) based on CT angiogram can accurately and precisely identify the target nidus as well as an interventional cerebral arteriogram.

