2.3 Endpoints

The primary endpoint of this study is to compare the target generated from interventional cerebral arteriography (reference) to targets generated from CT angiogram and MRI alone, to assess whether noninvasive imaging approaches are non-inferior to the UTSW standard.

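### Section 6.1.1 lets CTA inform the reference contour; in any patient where it does, CTA is judged partly against itself and Dice is expected to lean towards non-inferiority

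*Combined protocol and SAP*

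**What the plan says.** - **Reference.** Section 6.1.1 defines it as "AVM nidus identified using interventional cerebral arteriography superimposed to MRI of brain +/- CT angiography (CTA), per treatment team discretion", and adds that this is the contour used in the actual SRS treatment.
- **Test target.** The same section has the CTA target drawn from CTA alone, more than one month later and blinded, by the neurosurgeon who drew the reference.
- **Question asked.** The study summary asks whether a CTA-based plan can "accurately and precisely identify the target nidus as compared to standard cerebral arteriography fused to MRI". Section 1.3 sets out to "evaluate whether a target volume based on CT angiography can serve as a reliable substitute for a target based on interventional cerebral arteriography". The primary objective in 2.1 is whether CTA targets can "accurately and precisely identify the target nidus as well as an interventional cerebral arteriogram".
- **Endpoint.** Sections 2.3 and 9.1 describe the reference as the target generated from arteriography, and the aim as "to assess whether noninvasive imaging approaches are non-inferior to the UTSW standard". Section 6.1.2 also describes the reference as arteriography-derived, without mentioning CTA.
- **Use of CTA in planning.** Section 1.2 says the institution uses CTA at the team's "discretion to further enhance the accurate delineation of the final treatment" volume, but also that this had not been routine, because the benefit was uncertain and extra contrast burdens the kidneys. Section 4.1 now obtains CTA in every patient, for possible use in treatment as well as for the protocol's assessments.
- **Test.** Section 9.2 gives the only margin and test, both for Dice: one-sided t-test at 0.05, margin -0.077, 14 patients, 92% power.

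**The concern.** When the test under evaluation contributes to the reference standard, the two share information, and their agreement partly reflects that sharing. Here the reference may contain CTA and the test target is CTA alone. In an affected patient, Dice is expected on average to be higher than it would be against an arteriography + MRI contour, although any single contour need not move towards CTA. Higher Dice favours non-inferiority.

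Section 1.3 envisages that adequate agreement could lead future investigators to omit arteriography selectively. For that purpose the reader needs agreement with arteriography + MRI. The protocol requires neither a CTA-free contour nor a record of whether CTA informed the reference (the CRFs are not shown), and the data analysis section, 9.3, covers interim reports only. Without such a record, a reader of a positive result could not separate agreement with arteriography + MRI from agreement with a reference that already contained CTA.

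**Working it through.** **Inputs, all from section 9.2:** n = 14, SD = 0.0894, margin 0.077 in absolute value, one-sided alpha = 0.05, one-mean non-inferiority test. The share of patients with a CTA-informed reference and the resulting gain in Dice are not in the documents; both are assumed below.

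**Step 1: reproduce the stated power.** The critical value is t(0.95; 13 df) = 1.771. The noncentrality is 0.077 × √14 / 0.0894 = 3.22. The noncentral t gives P(T > 1.771) = 0.920, which matches the stated 92%. The sample size arithmetic is not in question.

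**Step 2: find the shift that doubles the error.** Suppose CTA's true mean Dice against an arteriography + MRI contour lies exactly on the non-inferiority threshold. The false non-inferiority rate is then 5%. Let the reference raise mean Dice by s. The noncentrality becomes s × √14 / 0.0894. Setting the rejection probability to 0.10 gives noncentrality 0.383, so s = 0.383 × 0.0894 / √14 = 0.00915. As a share of the margin this is 0.00915 / 0.077 = 11.9%. The result depends on s, SD and n, and not on where the threshold lies.

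**Step 3: express it per affected patient.** With k of 14 patients affected and gain d in each, the mean shift is s = k × d / 14. Simulation with k fixed, 1,000,000 runs per row:

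| Affected | Assumed gain d | Mean shift | False non-inferiority rate |
|---|---|---|---|
| 0 of 14 | none | 0 | 5.0% |
| 4 of 14 | 0.032 | 0.0091 | 9.6% |
| 7 of 14 | 0.018 | 0.0090 | 9.7% |

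The rates fall slightly below 10% because a gain in only some patients also adds a little spread.

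**Step 4: do the existing safeguards remove the shift?** The delay and blinding in 6.1.1 act when the CTA target is drawn. They limit the neurosurgeon's recall of the reference. They cannot take out CTA information that entered the reference on the treatment day.

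**The case against.** The strongest reply is that the treated contour is the intended comparator. Sections 2.3 and 9.1 name the institution's standard, 1.2 describes that standard as arteriography with MRI and discretionary CTA, and 6.1.1 says plainly that the reference is what was used for treatment. This stands in part. The choice may be deliberate, and in every patient whose contour did not use CTA the treated contour is the arteriography + MRI contour and answers the question asked. It does not help where CTA was used, because the substitution question in the study summary, 1.3 and 2.1 is then not cleanly answered.

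Second, CTA may seldom be used. Section 1.2 says it had not been routine. That is the documents' only evidence on frequency, and it counts against assuming a large share. It describes practice before this protocol, however, and 4.1 now makes CTA available in every patient.

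Three stronger readings are tempting and not supported:

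- A reader might infer from 4.1 that every reference contains CTA. The section shows availability, not use.
- A reader might see a contradiction between 6.1.1 and the statement in 1.3 that "Patients on this protocol will still get treated based on target generated by interventional cerebral arteriography but also receive CT angiography". That sentence does not say CTA is withheld from contouring; it and the wording of 6.1.2 can be read as shorthand for the definition in 6.1.1. The wording is incomplete rather than contradictory.
- A reader might extend the criticism to MRI, which is in every reference. Section 1.3 explains that arteriography "requires an MRI of the brain for the 3D information", so that overlap belongs to the standard itself.

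**Conclusion.** The point holds conditionally. Section 6.1.1 permits CTA in the reference; wherever that happens, Dice is expected on average to be biased towards agreement and the non-inferiority test is favoured. Little is needed to matter: an average shift of 0.009 in mean Dice, 12% of the margin, takes the false non-inferiority rate from 5% to 10%.

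That figure assumes a one-sample test against a fixed threshold, as section 9.2 sizes it. Section 9.2 also mentions Dice for both the invasive and the noninvasive approach, so the comparator is not wholly clear. The figure further assumes the plan's SD and a true mean on the threshold. It shows how sensitive the test is and does not estimate the bias: the actual shift cannot be derived from the documents and is nil if CTA is never used in the reference.

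The documents do not support the inference that the trial's result will be invalid, or that the treated contour can never answer the objective. Hausdorff distance would be expected to shrink for the same reason, but the plan gives it no margin or test, so no effect on a Hausdorff decision is claimed. This is a cheap improvement worth making.

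**What to change.** **Minimum.** Add one CRF field per patient recording whether CTA informed the treated contour (yes/no), and report the Dice and Hausdorff results split by that field. With 14 patients, and CTA use chosen by the team, the split is descriptive, but it shows the reader how far the issue arises.

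**Preferred.** In 6.1.1, define the primary analysis reference as an arteriography + MRI contour made without CTA, by one uniform procedure in all 14 patients. The same neurosurgeon redraws it under the delayed (more than one month), blinded procedure that 6.1.1 already uses, in a session more than one month apart from the CTA and MRI target sessions. Keep the treated contour as a pre-specified sensitivity comparison. Leave treatment, and any use of CTA in it, to the team. Align the wording of the study summary, 2.3, 6.1.2 and 9.1.

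Keep all 14 patients, so that power stays at 92%. Dropping those with a CTA-informed reference is not advised: by the calculation in step 1, power would fall to 87% with 12 patients, 81% with 10 and 64% with 7.

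**Cost.** One CRF field, one extra contour per patient (some neurosurgeon time) and one sensitivity analysis. There is no added imaging and no step on the treatment day. Some recall of the treated contour may persist in the redraw; the delay limits this but does not eliminate it.

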6.1.2 Evaluation and comparison of targets

Two methods of segmentation geometric accuracy evaluation, Dice coefficients and Hausdorff distance analysis, will be utilized to compare the reference target generated from interventional cerebral arteriography to targets generated from CT angiograms.

6.1.2.1 Dice Coefficients (DCs = $2(A \cap B) / (A + B)$), where A and B are the ground-truth and evaluated as segmented volumes, respectively. Dice coefficient is a simple spatial overlap index and a reproducibility validation metric¹⁶ and a reproducibility validation metric, which has been adopted to validate the segmentation of white matter lesions in MRI¹⁷ and brain tumors¹⁸. The value of a Dice Coefficients ranges from 0, indicating no spatial overlap between two sets of images, to 1, indicating complete overlap.

6.1.2.2 Hausdorff distance (HD) between two finite point sets A and B is defined by $HD(A, B) = \max(h(A, B), h(B, A))$, where $h(A, B) = \max_{a \in A} \min_{b \in B} \|a - b\|$. Spatial distance based metric, such as HD, is widely used in the evaluation of image segmentation when the segmentation overall accuracy, such as the boundary delineation (contour), of the segmentation is of importance¹⁹.

6.2 Safety/Tolerability

IV hydration will be initiated prior to all radiosurgery procedures and continued as needed until discharge. Patients will be instructed to increase hydration after the procedure and report to the treating physician in the event of developing decrease in urine output, new or worsening of swelling in extremities or around the eyes, fatigue, shortness of breath, chest pain or pressure, confusion or seizure to prevent kidney injury.

- Serum creatinine will be checked 1 week (-3 days/+7 days) after the procedure and again at 1 month (+/- 10 days) after the procedure.

7.0 ADVERSE EVENTS

7.1 Kidney Injury

7.1.1 Contraindications: Contrast allergy, underlying significant renal dysfunction or renal failure.

7.1.2 Special Warnings and Precautions for Use: The generally accepted safe upper limit total dose of iodinated contrast in one day is 225 mL of ISOVue-370 for adults and 125 mL for children between the ages of 10 to 18. The amount of the administered contrast may be exceeded at the knowledgeable direction of the treating radiologists.

7.1.3 Interaction with other medications: Nephrotoxic drugs, such as gentamycin, high-dose nonsteroidal anti-inflammatory drugs, or certain chemotherapeutic drugs.

7.1.4 Adverse Reactions: Sites-specific. Please see section 7.2.

